## 2. INTRODUCTION

The purpose of this statistical analysis plan (SAP) is to describe the planned analyses and data displays to be included in the Clinical Study Report (CSR) for Protocol AT-01B-004.

Protocol Revision Chronology:		
Protocol	Date	Original
Protocol	05-OCT-2022	Original
Amendment 1	09-JAN-2023	An editorial oversight prompted the deletion of “randomized” from the title of the protocol.
Amendment 2	15-AUG-2023	Add/revise language to comply with the European Union Clinical Trial Regulations. Aligns the populations for statistical analyses with the Statistical Analysis Plan and clarifies certain operational issues. Updated the numbers of subjects exposed to bemnifosbuvir and ruzasvir to align with the latest edition of the respective Investigator Brochures. Other minor clarifications.
Amendment 3	29-MAR-2024	Revise the study stopping rules based on feedback from the US FDA. Increases the number of subjects that are permitted to enroll in the optional pharmacokinetic (PK) and pharmacokinetic-viral kinetic (PK-VK) sub-studies. Other minor clarifications.

This SAP was developed in accordance with ICH E9 guideline. All decisions regarding final analysis, as defined in this SAP document, will be made prior to Database Lock. Further information can be found in the protocol.

The statistical analysis plan (SAP) is based on:

- Protocol No. AT-01B-004, Amendment 1, dated January 09, 2023
- ICH guidelines E4 and E9 (Statistical Principles for Clinical Trials)

The purpose of this document is to provide details on study populations and on how the variables will be derived, how missing data will be handled as well as details on statistical methods to be used to analyze the safety and efficacy data for study protocol No. AT-01B-004.

The document may evolve over time, for example, to reflect the requirements of protocol amendments or regulatory requests. However, the final SAP must be finalized, approved by the Sponsor, and placed on file before database is locked. Deviations from the final approved plan will be noted in the clinical study report.

### **3. STUDY OBJECTIVES AND ENDPOINTS**

#### **3.1. Study Objectives**

##### **3.1.1. Primary Objectives**

The primary objectives of this study are:

- To evaluate the safety and tolerability of BEM + RZR
- To evaluate the efficacy of BEM + RZR as assessed by the proportion of subjects achieving SVR12

##### **3.1.2. Secondary Objectives**

The secondary objectives of this study are:

- To evaluate the efficacy of BEM + RZR, as assessed by the proportion of subjects experiencing virologic failure (either on-treatment or post-treatment relapse [by 12 weeks post-treatment])
- To evaluate the efficacy of BEM + RZR as assessed by the proportion of subjects achieving SVR24

##### **3.1.3. Exploratory Objectives**

The exploratory objectives are:

- To evaluate the effect of baseline RAVs in NS5A and/or NS5B on the efficacy of BEM + RZR
- To evaluate the emergence of NS5A and NS5B RAVs in subjects who experience virologic failure
- To evaluate antiviral activity/viral kinetics (VK) of BEM + RZR
- To evaluate the PK and VK of BEM + RZR in the subgroup of subjects who agree to additional serial PK and VK sampling

### **3.2. Study Endpoints**

#### **3.2.1. Primary Endpoints**

The primary objectives of this study are:

- To evaluate the safety and tolerability of BEM + RZR
- To evaluate the efficacy of BEM + RZR as assessed by the proportion of subjects achieving SVR12

### **3.2.2. Secondary Endpoints**

Secondary efficacy endpoints include:

- Virologic failure
- SVR24

### **3.2.3. Exploratory Endpoints**

Exploratory endpoints include:

- Resistance to either study drug (BEM or RZR)
- SVR12 in subgroups defined by demographics and/or baseline characteristics
- HCV RNA changes from baseline
- Exposure-response relationships

Refer to Appendix 1 for RNA related derivations.

## 4. STUDY DESIGN

### 4.1. Summary of Study Design

AT-01B-004 is an open-label trial to evaluate 8 weeks of treatment with BEM + RZR in subjects with chronic HCV infection. Approximately 280 treatment-naïve subjects with genotype (GT) 1, 2, 3, 4, 5, 6, or 7, either without cirrhosis or with compensated cirrhosis, will be enrolled (Table 2).

[figure not shown]
**Table 2: Planned Study Enrollment**

Total Number	Genotype	Enrollment Targets	Fibrosis Stage
N = 280	1a	n = 75	F0-F4 (Target: 20% with compensated cirrhosis)
	1b	n = 40	
	2	n = 40	
	3	n = 75	
	4	n = 25	
	5, 6, or 7	n = 25	F0-F4 (No specified target for compensated cirrhosis)

A lead-in group of 60 non-cirrhotic subjects will initially be enrolled. At 4 weeks posttreatment, this lead-in group will be evaluated for safety, sustained virologic response at 4 weeks posttreatment (SVR4) and virologic relapse; enrollment will open to the remaining 220 subjects provided that  $\leq$  6 subjects in the lead-in group (from the Pill-Compliant per-protocol [PC-PP] population) experience virologic failure and no study stopping rules (Protocol Section 5.6) are met.

A schematic of the study design is presented in [Figure 1](#).

**Figure 1: Study Design**

a Can be extended to 6 weeks under extenuating circumstances with Sponsor approval.  
BEM = bemnifosbuvir; RZR = ruzasvir; SVR4 = sustained virologic response at 4 weeks posttreatment

## 4.2. Definition of Study Drugs

Study drug (550 mg BEM and 180 mg RZR) is to be administered once daily for 8 weeks, i.e., a total of 56 doses. Each dose will be taken as two (2) 275-mg tablets of BEM and two (2) 90-mg capsules of RZR.

## 4.3. Sample Size Considerations

### 4.3.1. Sample Size Justifications

The primary analysis will be based on the PK/PC-PP population. The sponsor expects approximately 95% of the enrolled subjects to meet the PK/PC-PP criteria (Section 6.5.5). Therefore, the PK/PC-PP population is expected to be 71 subjects with GT3 infection, and 266 subjects across all genotypes based on target enrollment provided in Table 3.

Table 3 displays the lower one-sided 95% confidence bounds for a range of potential observed outcomes based on these sample sizes. The table indicates that an observed overall SVR rate in excess of 95% would provide high confidence that the true overall SVR rate is at least 93%. This assumes homogeneity of effect across genotypes. Confidence bounds based on the target genotype 3 enrollment are also presented and these indicate that an observed rate greater than 95% in genotype 3 subjects would provide high confidence that the true SVR rate in genotype 3 subjects is at least 90%.

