### **8.4. Efficacy Analyses**

#### **8.4.1. Primary Analyses**

In this analysis, results are pooled across genotypes and cirrhosis status as it is expected that efficacy will be consistent across these groups. To evaluate the robustness of results, additional analyses, including summarization by genotype and cirrhosis status, will be carried out.

The proportions of subjects in the PP population(s) achieving SVR12 will be estimated and presented with associated two-sided 95% confidence intervals (CIs), which will be constructed using the Wilson score method. Reasons for failure to achieve SVR12 will be summarized.

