**Table 3: Lower One-sided 95% Confidence Bounds Associated with Observed Outcomes**

Observed SVR rate	N=266 evaluable (overall)	N=71 evaluable (GT3 target) a
90%	87%	83%
91%	88%	
92%	89%	84%
93%	90%	86%
94%	91%	88%
95%	92%	
96%	93%	90%
97%	95%	92%
98%	96%	

Values are rounded to nearest whole percentage.

a Shaded box indicates observed SVR not attainable with N=71.

GT3 = genotype 3; SVR = sustained virologic response

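### An observed overall SVR rate just above 95% does not give a one-sided 95% lower bound of 93%: the sponsor's own table shows 92% at 95%, and 93% needs about 96% (255 of 266)

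*SAP*

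**What the plan says.** SAP 4.3.1 and Protocol 8.8 justify the size of the trial by precision. The SAP starts from an evaluable fraction, "The sponsor expects approximately 95% of the enrolled subjects to meet the PK/PC-PP criteria", so that "the PK/PC-PP population is expected to be 71 subjects with GT3 infection, and 266 subjects across all genotypes". Protocol 8.8 uses the same numbers for its per-protocol population.

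Both documents then give a table (SAP Table 3, Protocol Table 5) titled "Lower One-sided 95% Confidence Bounds Associated with Observed Outcomes", with the footnote "Values are rounded to nearest whole percentage". The rows that matter are:

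| Observed rate | Bound, N=266 | Bound, N=71 |
|---|---|---|
| 95% | 92% | blank (not attainable) |
| 96% | 93% | 90% |

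The text draws two conclusions from the table. Overall: "an observed overall SVR rate in excess of 95% would provide high confidence that the true overall SVR rate is at least 93" percent. For genotype 3, a result "greater than 95% in genotype 3 subjects would provide high confidence that the true SVR rate in genotype 3 subjects is at least 90" percent.

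For the analysis itself, Protocol 8.4.1 says that the SVR12 proportions will be "presented with associated two-sided 95% confidence intervals (CIs), which will be constructed using the Wilson score method". SAP 8.4 plans no hypothesis test.

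**The concern.** The overall sentence sets a threshold: any result above 95% should support a true rate of at least 93%. The table printed beside it shows 92% at 95%, so results only slightly above 95% look unlikely to reach 93%. The sentence and the table are also built on a one-sided bound, whereas the study report will show the lower limit of a two-sided interval.

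The trial has no power calculation and no hypothesis test. These two sentences are therefore the only account of what about 266 and 71 evaluable subjects can show about the true SVR rate. If the overall result fell just above 95%, the report could repeat the planning statement next to a printed lower limit more than one point below it. Nothing operational depends on the sentences.

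**Working it through.** **Inputs.** Enrolment is about 280 overall and 75 in genotype 3 (SAP Table 2). The evaluable fraction is 95% (SAP 4.3.1). Sidedness and rounding come from the title and footnote of SAP Table 3. The reported interval is the two-sided 95% Wilson interval (Protocol 8.4.1).

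**Evaluable numbers.** 280 × 0.95 = 266, and 75 × 0.95 = 71.25, taken as 71. Both agree with the plan.

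**Formula.** With p = x/n, the Wilson lower limit is

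L = [p + z²/(2n) − z·√(p(1−p)/n + z²/(4n²))] / (1 + z²/n),

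with z = 1.645 for the one-sided 95% bound and z = 1.960 for the lower limit of the two-sided 95% interval.

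**Reproducing the table.** Taking the count nearest each nominal rate, the one-sided Wilson bound, rounded to a whole percent, matches 14 of the 15 filled cells. The remaining cell (90%, N=266, stated as 87%) matches with 240/266 (86.81%) or with exactly 90.0% (86.56%). The exact (Clopper-Pearson) bound fits the overall column but misses three genotype 3 cells: 82.28%, 89.44% and 91.40% against the stated 83%, 90% and 92%. So the table is one-sided 95% Wilson, and it is sound.

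**Overall sentence.** 95% of 266 is 252.7, so 253 is the smallest count above 95%. For 253/266, p = 0.95113:

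- p + z²/(2n) = 0.95621
- the square-root term multiplied by z = 0.02233
- 1 + z²/n = 1.01017
- L = (0.95621 − 0.02233)/1.01017 = 0.9245

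The same calculation at each count, for both values of z:

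| Count | Observed | One-sided 95% bound | Two-sided 95% lower limit |
|---|---|---|---|
| 253/266 | 95.11% | 92.45% | 91.82% |
| 254/266 | 95.49% | 92.90% | 92.28% |
| 255/266 | 95.86% | 93.35% | 92.75% |
| 256/266 | 96.24% | 93.81% | 93.22% |

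Two attainable results above 95% have one-sided bounds below 93%. The first shows as 92% even after rounding; the second reaches 93% only by rounding. The largest shortfall is 93 − 92.45 = 0.55 point. The first count that truly reaches 93% is 255 on the one-sided bound and 256 on the two-sided limit.

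**Genotype 3 sentence.** 67/71 is 94.37%, so 68/71 is the smallest attainable result above 95%.

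| Count | Observed | One-sided 95% bound | Two-sided 95% lower limit |
|---|---|---|---|
| 68/71 | 95.77% | 89.89% | 88.30% |
| 69/71 | 97.18% | 91.84% | 90.30% |

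68/71 is the table's 96% row, shown as 90%. The sentence therefore follows from the rounded table; unrounded, it falls short by 90 − 89.89 = 0.11 point.

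**Against the interval to be reported.** At the smallest qualifying results, the stated figures exceed the two-sided lower limits by 93 − 91.82 = 1.18 points overall and 90 − 88.30 = 1.70 points in genotype 3.

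**The case against.** The best defence of the overall sentence is that a rate above 95% means the next row of the table, 96%, which does read 93%. On that reading only 253/266 misses 93% at the table's own rounding, and the issue is loose wording. This limits the size of the point but does not remove it. The sentence gives a threshold, not a row, and both 253/266 and 254/266 lie above 95% but nearest the 95% row.

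The defence is right about several stronger readings that a reader might infer:

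- *That the genotype 3 sentence contradicts the table.* It does not. The 95% cell is blank because no count out of 71 gives that rate, and the next attainable result is the row that reads 90%.
- *That the claims are arithmetically wrong by 1.2 and 1.7 points.* Those gaps appear only on moving to a two-sided limit. The table and the text openly say one-sided, and on that basis the gaps are 0.55 and 0.11 point.
- *That the reported interval would rule out the claims.* At 253/266 the two-sided interval is about 91.8% to 97.1%, and at 68/71 about 88.3% to 98.6%. Each contains the claimed value and much above it. The interval fails to exclude lower rates, which is a different matter.
- *That these are the only benchmarks in the plan.* The lead-in rule, which closes enrolment if virologic failure exceeds 10% (SAP 5.1, Protocol 8.7), is a benchmark, and an operative one. The sample-size sentences trigger nothing.

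It is also fair to say that a descriptive study may plan on a one-sided bound and report a two-sided interval. That is allowed, but the documents should say so where the benchmark is stated.

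**Conclusion.** The overall sentence is overstated as written. On the documents' own one-sided 95% Wilson basis, the 93% bound needs at least 255/266 (95.9%), and the shortfall just above 95% is at most about 0.55 point. The genotype 3 sentence is consistent with the rounded table and holds only by rounding (89.89% at 68/71).

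The planning statement also does not describe the interval that will be reported. On that interval, 93% overall needs at least 256/266 (96.2%) and 90% in genotype 3 needs at least 69/71 (97.2%). This second part is a mismatch of sidedness, not an error of calculation.

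The counts assume exactly 266 and 71 evaluable subjects. Both are expectations, resting on about 280 enrolled and about 95% evaluable, so the exact counts will shift with the realised numbers. The overall figure also relies on the plan's own assumption that the effect is the same across genotypes.

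**What to change.** In SAP 4.3.1 and Protocol 8.8:

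1. Restate the overall sentence: an observed rate of about 96% or more (at least 255/266) gives a one-sided 95% lower bound of at least 93%.
2. Say that in genotype 3 the smallest attainable rate above 95% (68/71, 95.8%) gives a one-sided bound of about 90% (89.9%).
3. Add to the table the lower limits of the two-sided 95% Wilson interval, and note that on that interval at least 256/266 (96.2%) is needed for 93% and at least 69/71 (97.2%) for 90%.
4. Name the Wilson method in the table, and note that 266 and 71 are expected numbers, so the limits will be recalculated on the subjects actually analysed.

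The cost is one paragraph and one table in each document, and a slightly less favourable stated threshold. No extra subjects are needed, and the analysis and all decision rules stay as they are.

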**Table 3: Lower One-sided 95% Confidence Bounds Associated with Observed Outcomes**

Observed SVR rate	N=266 evaluable (overall)	N=71 evaluable (GT3 target) a
90%	87%	83%
91%	88%	
92%	89%	84%
93%	90%	86%
94%	91%	88%
95%	92%	
96%	93%	90%
97%	95%	92%
98%	96%	

Values are rounded to nearest whole percentage.

a Shaded box indicates observed SVR not attainable with N=71.

GT3 = genotype 3; SVR = sustained virologic response

#### 4.3.2. Sample Size Re-Estimation

No sample size re-estimation is planned in this study.

#### 4.4. Randomization

This is an open-label one arm study. No randomization is planned.

#### 4.5. Clinical Assessments

The following assessments will be performed at Screening, with a window for up to 4 weeks prior to the first dose of study drug. This can be extended for up to 6 weeks for extenuating circumstances with sponsor approval.

- Demographics
- Medical history
- Complete physical examination
- Vital signs
- Height and weight
- Triplicate 12-lead ECGs
- Fibrosure (Fibrotest) and APRI, Liver biopsy, FibroScan (if needed)
- Clinical labs and urinalysis

- HBV, HCV, and HIV screen; hemoglobin A1c
- Pregnancy test (females of childbearing potential)
- HCV genotyping
- Viral resistance
- HCV RNA quantitation (PCR)

During the treatment period, viral resistance and HCV RNA PCR samples will be collected corresponding to Day 1, 8, 15, 29, 43, 57, early termination (ET), and follow-up visits (week 4, 12, and 24).

PK samples will be collected corresponding to Day 1 (predose), 8, 15, 29, 43, 57, and ET. In subjects who opt-in for the optional serial PK-only substudy, additional PK samples will be collected on a single occasion during any planned treatment-period visit as early as week 2 at 0.5 ( $\pm$  15 minutes), 1 ( $\pm$  15 minutes), 2, 3, 4, 6 and 8 hours postdose (results from the predose PK sample collected as part of the main study will be used as the predose timepoint in the substudy analysis). In subjects who opt-in for the optional serial PK/VK substudy, additional PK/VK (HCV RNA) samples will be collected on Day 1 at 0.5 ( $\pm$  15 minutes), 1 ( $\pm$  15 minutes), 2, 3, 4, 6, 8 hours postdose (results of the Day 1 predose PK/VK (HCV RNA) samples collected as part of the main study will be used as the predose timepoint in the substudy analysis), and predose on Days 2 and 3.

Information on study drug administration will be recorded on Day 1, and subjects may be contacted between visits to assess compliance, concomitant medications, and AEs/SAEs.

## 5. PLANNED ANALYSES

### 5.1. Interim Analyses

An interim analysis will be performed on data from the lead-in group using the PP population. The proportion of subjects achieving SVR4, defined as HCV RNA < lower limit of quantification [LLOQ] at 4 weeks posttreatment, will be presented with 2-sided 95% confidence intervals (CIs) using the Wilson score method. Virologic failure, defined as either on-treatment failure or posttreatment relapse by 4 weeks posttreatment, will also be estimated and presented with 95% CIs. A virologic failure rate of >10% (> 6 subjects in the lead-in group) will close the study to further enrollment. Safety will also be evaluated, including AEs and clinical laboratory evaluations. The study will also be closed to further enrollment if any study stopping rules are met (Protocol Section 5.6.3).

The interim analysis will include the lead-in group of patients. The interim analysis will be conducted after at least 60 patients have reached their week 4 post-treatment visit or have experienced early VF.

### 5.2. Final Analyses

The primary analysis will be performed after all participants have completed the assessments for SVR12 or discontinued from the study and all data through 12 weeks post treatment period have been cleaned and finalized.

A Week 24 Follow-up analysis to evaluate the data collected through 24 weeks post treatment period will be performed when all subjects have completed or discontinued from the study and data cleaning has been completed.

## **6. GENERAL CONSIDERATIONS FOR DATA ANALYSES AND HANDLING**

### **6.1. General Summary Table and Individual Subject Data Listing Considerations**

Unless otherwise specified, continuous variables will be summarized by using the number of non-missing observations, arithmetic mean, standard deviation (SD), minimum, first quartile, median, third quartile and maximum values as summary statistics; categorical variables will be summarized by using the frequency count and the percentage of subjects in each category as summary statistics.

When a summary tabulates the number of subjects, subjects will only be counted once for a category (e.g., a particular adverse event type, a particular adverse event term, a particular concomitant medication) unless otherwise specified.

### **6.2. General Post Text Summary Table and Individual Subject Data Listing Format Considerations**

By-subject listings will be sorted by subject ID number, assessment/start date, and assessment/start time (where applicable).

### **6.3. Data Management**

Source documents will be used to record all study-related data. Designated site staff will use the source document entries to enter the data required by the protocol into the eCRFs.

Site staff will be trained on accessing and using the web-based EDC system. Investigational site staff will not be given access to the EDC system until the required training is completed and documented. One eCRF casebook will be completed for each subject enrolled in the study. All source data and eCRFs will be reviewed, evaluated, and signed by the investigator (or designee), as required.

The original source documents and a copy of the corresponding casebook will be retained by the investigator.

Data from eCRFs and other external data (e.g., laboratory data) will be entered into the eCRF or merged with a clinical database as specified in the data management plan. Quality control and data validation procedures will be applied to ensure the validity and accuracy of the clinical database.

In accordance with the vendor's applicable data management procedures, the clinical database will be reviewed and checked for omissions, apparent errors, and values requiring further clarification using computerized and manual checks and listings. Data queries requiring clarification will be issued in the eCRF and sent to the study site for resolution. Only authorized personnel will make corrections to the clinical data in the eCRF, and all corrections will be documented in an audit trail.

## **6.4. Data Presentation Conventions**

### **6.5. Analysis Populations**

#### **6.5.1. Screened Patients**

Screened Patients will include subjects who have signed the study informed consent.

The disposition of these patients will be summarized. For subjects who have failed to meet the inclusion/exclusion criteria reasons for failure will be listed.

#### **6.5.2. Safety Population**

The safety population will include all subjects who received at least one dose of the study drug (BEM or RZR).

Efficacy analyses will be performed for this population.

#### **6.5.3. Efficacy Evaluable Per-Protocol (EE-PP) Population**

The Efficacy Evaluable population will include subjects who:

1. Met all inclusion/exclusion criteria.
2. Did not receive concomitant medications that are prohibited due to their potential impact on HCV viral load or the pharmacokinetic concentration of either agent (BEM or RZR).
3. Have a collected or imputed (per Table 5) posttreatment viral load assessment at post treatment week 12, unless the subject discontinues early for virologic failure or AE, in which case the ET visit assessment may be used.
4. Has received at least one dose of study drug.

#### **6.5.4. Pill Compliant Per-Protocol (PC-PP) Population**

The Per-Protocol Population will include subjects who:

1. Met all inclusion/exclusion criteria.
2. Did not receive concomitant medications that are prohibited due to their potential impact on HCV viral load or the pharmacokinetic concentration of either agent (BEM or RZR).
3. Have a collected or imputed (per Table 5) posttreatment viral load assessment at post treatment week 12 (week 4 for the lead-in analysis), unless the subject discontinues early for virologic failure or AE, in which case the ET visit assessment may be used.
4. Completed treatment, discontinued treatment early due to virological failure, or discontinued treatment early due to drug-related AE.
  - Completed treatment is defined as being in  $\geq 90\%$  compliance with the study drug regimen and was on treatment for a minimum of 51 days. Compliance will be calculated using drug compliance data collected on the eCRF.

The sponsor expects approximately 95% of the enrolled subjects to meet these criteria.

All efficacy analyses will be performed on this population.

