### 3. STUDY DESIGN

#### 3.1. General Study Design

This is an open-label trial to evaluate 8 weeks of treatment with BEM + RZR in subjects with chronic HCV infection (Figure 2). Approximately 280 treatment-naïve subjects with genotype (GT) 1, 2, 3, 4, 5, 6, or 7, either without cirrhosis or with compensated cirrhosis, will be enrolled.

A lead-in group of 60 non-cirrhotic subjects will initially be enrolled. At 4 weeks posttreatment, this lead-in group will be evaluated for safety, SVR4, and virologic relapse; enrollment will open to the remaining 220 subjects provided that **CCI** [REDACTED] in the lead-in group experience virologic failure that was not due to poor compliance and no study stopping rules are met (Section 5.6.3).

**Figure 2:** Study Design

a Can be extended to 6 weeks under extenuating circumstances with Sponsor approval.  
BEM = bemnifosbuvir; RZR = ruzasvir; SVR4 = sustained virologic response at 4 weeks posttreatment

Subjects will be screened for up to 4 weeks, although this can be extended for up to 6 weeks for extenuating circumstances with Sponsor approval. Such circumstances may include awaiting reporting of laboratory results or scheduling assessment of cirrhosis (eg, FibroScan®) if needed. Re-screens may be approved on a case-by-case basis by the Sponsor (re-screened subjects will be assigned a new subject number).

At the end of the screening period (Baseline; Day 1), eligible subjects will enter the treatment period and receive BEM + RZR for 8 weeks. After Day 1 during the treatment period, subjects

may self-administer study drugs (ie, IMP) at home, with the exception of subjects who agree to additional PK and/or PK-VK blood sampling as part of up to two substudies. These subjects will be required to take their study drug in the clinic on certain days (see [Table 3](#)).

Subjects will return to the clinic for evaluations at Weeks 1, 2, 4, 6, and 8 (End of Treatment [EOT]) during the treatment period.

Following their last visit of the treatment period (including subjects who prematurely discontinue treatment) subjects will enter the Follow-up period and return to the clinic for evaluations at Follow-up Weeks 4, 12, and 24. End-of-Study (EOS) is defined as the visit at 24 weeks posttreatment.

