#### **8.1.3. Per Protocol Population**

The PP population will consist of all subjects who:

- Meet all inclusion/exclusion criteria
- Do not receive concomitant medications that are prohibited due to their potential impact on HCV viral load or the pharmacokinetic concentration of either agent (BEM or RZR)
- Have a collected or imputed posttreatment viral load assessment at posttreatment Week 12 (posttreatment Week 4 for lead-in subjects) unless the subject discontinues early for virologic failure or AE, in which case the ET visit may be used
- Complete treatment (being in  $\geq 90\%$  compliance with the study drug regimen), discontinue treatment early due to virological failure or discontinue treatment early due to a drug-related AE

*Note: Compliance will be calculated using drug compliance data collected on the eCRF.*

The Sponsor expects approximately 95% of the enrolled subjects to meet these criteria.

This population will be used for all efficacy analyses.

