## 8.7. Interim Analyses

An interim analysis will be performed on data from the lead-in group using the PP population(s). The proportion of subjects achieving SVR4, defined as HCV RNA < LLOQ at 4 weeks posttreatment, will be presented with 2-sided 95% CIs using the Wilson score method. Virologic failure, defined as either on-treatment failure or posttreatment relapse by 4 weeks posttreatment, will also be estimated and presented with 95% CIs. A virologic failure rate of >10% that is not due to poor compliance (>CCI in the lead-in group) will close the study to further enrollment.

Safety will also be evaluated, including AEs and clinical laboratory evaluations. The study will also be closed to further enrollment if any study stopping rules are met (Section 5.6.3).

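### The SAP's lead-in enrollment gate drops the protocol's poor-compliance condition, and PC-PP membership does not replace it for subjects stopped early for virologic failure

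*SAP*

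**What the plan says.** Protocol 3.1 makes opening enrollment to the remaining 220 subjects depend on how many subjects "in the lead-in group experience virologic failure that was not due to poor compliance". The synopsis, 1.4 and 3.2 repeat that condition, and 8.7 gives the closing rule as "A virologic failure rate of >10% that is not due to poor compliance". The number of failures allowed is redacted in the protocol.

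The protocol applies this rule to its PP population(s). Under 8.1.3 a subject qualifies by completing treatment at 90% compliance or better, or may "discontinue treatment early due to virological failure or discontinue treatment early due to a drug-related AE". The last two routes carry no compliance requirement.

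The SAP states the gate twice:

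- **SAP 4.1** opens enrollment if at most 6 "subjects in the lead-in group (from the Pill-Compliant per-protocol [PC-PP] population) experience virologic failure" and no stopping rule is met.
- **SAP 5.1** closes enrollment at a failure rate above 10%, glossed as more than 6 lead-in subjects. It refers to the PP population, although the SAP defines three per-protocol populations (6.5.3 to 6.5.5).

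Neither SAP passage mentions poor compliance as a reason not to count a failure.

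Criterion 4 of PC-PP (SAP 6.5.4) reads "Completed treatment, discontinued treatment early due to virological failure, or discontinued treatment early due to drug-related AE". The sub-bullet with the 90% compliance and 51-day minimum defines completed treatment only.

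**The concern.** The SAP appears to rely on the pill-compliant population to do what the protocol does with an explicit condition. That works for a non-adherent subject who reaches the end of treatment, who fails the 90% test and leaves PC-PP. It does not work for a non-adherent subject who breaks through on treatment. Protocol 5.6.1 stops every subject with confirmed on-treatment failure whatever the cause, and stopping for that reason is enough to enter PC-PP. The failure then counts toward the gate, although the protocol says that a failure due to poor compliance should not.

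At stake is the decision on whether the remaining 220 subjects are enrolled. Two governing documents can give opposite answers on the same data.

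**Working it through.** **1. The plan's own threshold.** The lead-in has 60 subjects (SAP 4.1). 0.10 × 60 = 6, and the smallest count above 10% is 7 (7/60 = 11.7%). The SAP's gloss of more than 6 reproduces.

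**2. Where a non-adherent lead-in subject ends up.**

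| Course | In PC-PP? | Counted under SAP 4.1? | Counted under the protocol condition? |
|---|---|---|---|
| Finishes below 90%, cured | No | No | No (not a failure) |
| Finishes below 90%, relapses | No | No | No |
| Stopped for noncompliance itself | No | No | No |
| Breaks through because of poor compliance, stopped for virologic failure | Yes | **Yes** | **No** |

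The documents part only in the last row. The protocol's PP population has the same open route (8.1.3), yet 8.7 uses that population and still adds the condition. So PP membership was not meant to stand in for the condition, and the SAP kept the population while losing the condition. Nothing else in the SAP removes such a subject: 5.1 counts on-treatment failure as virologic failure, and Table 5 scores early discontinuation for virologic failure as a failure.

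**3. A case where the decisions differ.** Take six compliant failures and one breakthrough due to poor compliance.
- Protocol condition: count = 6, not more than 6, so enrollment opens.
- SAP: count = 6 + 1 = 7, more than 6, so enrollment closes.

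The threshold of 6 is the SAP's.

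**4. Illustrative size.**

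Inputs:
- Evaluable subjects: 57, from 0.95 × 60, the share the sponsor expects to meet PC-PP (SAP 6.5.4).
- Compliant-failure rate p: assumed at 3%, 5% and 7%, since the documents give none.
- Number k of poor-compliance breakthroughs: assumed at 0, 1 and 2, and placed inside the 57.

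Under the SAP, enrollment closes if compliant failures plus k reach 7:

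P(close | k) = P(X ≥ 7 − k), with X ~ Binomial(57 − k, p).

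| p | k = 0: P(X ≥ 7), n = 57 | k = 1: P(X ≥ 6), n = 56 | k = 2: P(X ≥ 5), n = 55 |
|---|---|---|---|
| 3% | 0.2% | 0.7% | 2.4% |
| 5% | 2.3% | 6.0% | 14.0% |
| 7% | 10.2% | 19.6% | 34.1% |

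The k = 0 column is the reference with no such failure counted. Where breakthroughs do occur, the protocol condition would give slightly less than that column, because only 57 − k subjects could add a compliant failure. With all 60 evaluable, the 5% row becomes 3.0%, 7.4% and 16.4%.

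**5. A related ambiguity.** If PC-PP is the denominator and holds 57 subjects, 6/57 = 10.5% exceeds 10% without exceeding 6 subjects. The rate and the count in SAP 5.1 then disagree. Step 4 uses the count.

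**The case against.** The strongest reply is that the population rule is not a SAP departure. The protocol's PP and PK-PP populations have the same three routes and tie the 90% test to completing treatment. That is correct, and it limits the point to the missing gate condition.

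The probabilities are also illustrative. Neither document gives a failure rate or a frequency of non-adherent breakthrough, and at 3% one such subject moves the chance of closing only from 0.2% to 0.7%. That stands too. The conflict itself does not depend on these figures.

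Stronger readings a reader might infer are not supported:

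- **The SVR12 estimate is biased by retaining these subjects.** Keeping failures is conservative, and both documents share the rule. SVR12 is also analysed in EE-PP, which has no compliance test, and in the safety population.
- **Failures are the only non-compliant subjects in these populations.** Subjects stopped for a drug-related AE also enter without a compliance test, and SAP Table 5 gives them their 12- or 24-week post-treatment result, so they can be successes.
- **The trial would be closed.** The stated consequence is no further enrollment.
- **Any failure below 90% compliance up to the last dose should leave the count.** The protocol states no such cut-off. Two missed doses of 15 give 13/15 = 86.7%, so a genuine early drug failure could drop out of a gate that protocol 1.4 presents as a way to limit treatment failures.

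**Conclusion.** The point holds as a conflict between the two documents on a decision rule. The SAP omits the protocol's compliance condition in both statements of the gate, and PC-PP leaves the gap open for subjects stopped early for on-treatment virologic failure. Each such failure that is due to poor compliance uses one of the six allowed, and a single one can reverse the enrollment decision when compliant failures stand at six.

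The conflict follows from the text alone. Its probability rests on the assumed rates above, on 57 evaluable subjects and on the SAP's threshold. The protocol does not define when a failure is due to poor compliance or who decides, so its own rule is also not fully operational.

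The SAP contents page carries version 3.0, December 2024, and the documents do not show whether the lead-in decision had already been taken. If it had, the value of the correction is in reporting which rule was applied.

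**What to change.** Reconcile the passages in the SAP:

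1. Restore the protocol's poor-compliance condition in 4.1 and 5.1, and say that it also applies to subjects stopped early for virologic failure.
2. Prespecify how a failure is attributed to poor compliance and who decides, using the pill counts collected at each visit (protocol 5.4.4), without adding a fixed cut-off that the protocol does not contain.
3. In 5.1, name PC-PP in place of the PP population, and say whether the count or the rate governs when fewer than 60 subjects are evaluable.
4. List separately the lead-in failures not counted, with their compliance data.

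Leave the SVR12 populations and denominators as they are. The cost is a few lines of SAP text, one attribution flag and one listing, with no new data collection. If the gate has already been applied, state in the study report which rule was used and whether any failure was left out on compliance grounds.
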